Appendix 1: Documentation

Cue Health Privacy Policy

Cue Health Terms of Use and End User License Agreement

FDA Emergency Use Authorization Letter

Cue COVID-19 Test Instructions for Use

Cue Health Monitoring System Quick Start Guide

Cue Health Monitoring System User Manual

CareEvolution MyDataHelps Privacy and Use Policy

Cue Care Terms of Use

Appendix 2: Compatible Devices

- Apple®
 - Apple® iPhone® 8 Plus or later with iOS® 13 or higher
 - Apple® iPad® models with iPadOS® version 13.0 or higher with Bluetooth® Standard 4.2 or later (Bluetooth® 5.0 preferred)
 - iPad 6th generation or later
 - iPad Air® 3rd generation or later
 - iPad mini® 5th generation or later
 - iPad Pro® 2nd generation or later
- Android[™]
 - Smartphone models with OS 9.0 (API level 28) or higher; display size 5.5" or higher; Bluetooth® Standard 4.2 or later (Bluetooth 5.0 preferred); Wi-Fi® dual-band 2.4GHz and 5 GHz (5 GHz preferred).
 - O Any Android™ smartphone device which meets the above minimum requirements may be used. The following are recommended devices that meet these requirements:
 - Google Pixel[™] 4, 4a, 5, 6
 - Samsung Galaxy® A21, A71 5G unlocked, S8/S8+/S8 Note and later
 - Motorola® Moto G fast

Appendix 3: Participant Surveys

Note: Email is being collected at the time of screening and will be used to contact participants if there are changes in their eligibility status.

Eligibility Survey

Please complete the following survey to determine your eligibility for participation in this study.

- 1. Can you read and understand English? (Yes/No)
- 2. Are you over the age of 18? (Yes/No)
- 3. Are you 65 years or older? (Yes/No)
- 4. Do you live in the United States? (Yes/No)
- 5. Do you have a smartphone with a recent operating system installed (Android: OS 9.0 or higher, Apple: iOS 13.0 or higher)? (Yes/No)
- 6. Are you willing to connect your health insurance claims to the study app? (Yes/No) Tap the info icon for a list of health plan providers.
 - a. List that appears if the info icon is tapped:
 - b. Medicare
 - c. Medicaid
 - d. Anthem BlueCross and BlueShield
 - e. Anthem BlueCross
 - f. Empire BlueCross BlueShield
 - g. Empire BlueCross
 - h. Wellpoint
 - i. Carelon
 - j. Unicare
 - k. Simply Healthcare Plans
 - I. National Government Services, Inc.
 - m. MMM
 - n. Health Sun
 - o. HealthLink
 - p. Amerigroup
 - q. None of these
- 7. Are you immunocompromised? (Yes/No)

7a. If Yes \rightarrow Please classify your diagnosis. (Select all that apply.)

- Symptomatic HIV
- Graft versus host disease
- Immunoglobulin deficiency/Immunodeficiency
- Immunosuppressive therapy
- Leukemia
- Lymphoma (Hodgkin or non-Hodgkin)

- Metastatic Cancer
- Multiple Myeloma
- Solid organ malignancy, with immunosuppression
- Transplant, hematopoietic stem cell
- Transplant, solid organ
- None of these
- 8. Are you able to upload verification of your immunocompromised status, if necessary? This can be a screenshot of an EMR (electronic medical record), diagnosis list, or a doctor's note. (Yes/No)
- 9. Have you completed a COVID-19 vaccine primary series? (Yes/No)
 - If you have a medical exemption for COVID-19 vaccination, please email the study team at [contact]
- 10. One more thing, will you share your email or phone number? We will contact you if there is a change to your eligibility status. This is optional at this point.
 - a. What is your phone number or email address?
- If 1, 2, 4, and 5 are YES and either
 - 1. 3 is yes, 6 is yes, and 6a is not "None of these"
 - 2. 7 is yes and 7a is not "None of these"

then:

If 1 through 8 are YES and 6a is not "None of these": Thank you! You are **eligible** to participate. Please continue to learn more about our study.

Otherwise: Thank you for your interest in participating in the ImmunoCARE Study. Unfortunately, you did not meet the study's eligibility requirements at this time.

Baseline Survey

Thank you for consenting to participate in this study. Please complete this baseline survey.

- 1. What is your date of birth?
- 2. What is your phone number?
- 3. In case we cannot contact you, please provide the telephone number of a relative or friend who would know where you can be reached. This is optional.
- 4. What terms best express how you describe your gender identity? (Check all that apply)
 - Man
 - Woman
 - Transgender
 - Non Binary
 - Other (please specify)
 - Prefer not to answer
- 5. Which categories describe you? Select all that apply. Note, you may select more than one group
 - American Indian or Alaskan Native
 - Asian
 - o Black, African American, African
 - o Hispanic, Latino, or Spanish
 - Middle Eastern or Northern African
 - Native Hawaiian or other Pacific Islander
 - o White
 - None of these fully describe me (please specify)
 - o Prefer not to answer
- 6. What is your annual household income from all sources?
 - \$25,000 or less
 - More than \$25,000
- 7. What is your zip code?
- 8. Please indicate if you have any of the following chronic conditions
 - Diabetes
 - High blood pressure
 - Asthma
 - o COPD
 - Emphysema
 - Chronic Bronchitis
 - Heart Failure
 - Chronic Kidney Disease
 - Other (please specify)
- 9. How many doses of the COVID-19 vaccine have you received?

reviewed by the study team. 10. For your [nth] dose, please indicate: Date Type: [] Full dose [] Booster Manufacturer: [] Pfizer [] Moderna [] Janssen (Johnson & Johnson) [] Novavax [] Other (if you received it abroad) [Repeats for the number of doses reported in 7.] 11. Over the last month have you: Been exposed to a close contact with COVID-19? [] Yes [] No Contracted COVID-19? [] Yes [] No [] Yes [] No Been prescribed medication for COVID-19? [] Yes [] No Been to Urgent Care due to COVID-19? [] Yes [] No Been to the Emergency Room due to COVID-19? [] Yes [] No Been admitted to the hospital for COVID-19? Been in the Intensive Care Unit due to COVID-19? [] Yes [] No o Needed additional health care (e.g. dialysis, CT scan, MRI) as a result of COVID-19? [] Yes [] No Is there any context you would like to share about the responses above? (open text box) Monthly Survey Thank you for your continued participation in the ImmunoCARE study. This survey is intended to capture information about how you have been feeling and any COVID-19 exposures and infections you have had since we last checked in. Once you complete this survey you will earn a \$10 Amazon gift card to thank you for your time. 1. Since we last checked in, have you: Been exposed to a close contact with COVID-19? [] Yes [] No Contracted COVID-19? [] Yes [] No Been prescribed medication for COVID-19? [] Yes [] No [] Yes [] No Been to Urgent Care due to COVID-19? Been to the Emergency Room due to COVID-19? [] Yes [] No

Been admitted to the hospital for COVID-19?

If none: please confirm your medical exemption from COVID-19 vaccination was

[] Yes [] No

0	Been in the Intensive Care Unit due to COVID-19?	[] Yes	[] No
0	Needed additional health care (e.g. dialysis, CT scan,	MRI) as a	result of
	COVID-19?		
		[] Yes	[] No

Is there any context you would like to share about your previous responses? (open text box)

Thank you for sharing this information with the study team. Your Amazon gift card is now available.

If No \rightarrow Thank you for confirming you have not had COVID-19 since we last checked in. Your Amazon gift card is now available.

End of Study Survey

Thank you for your participation in the ImmunoCARE study. This survey is intended to capture information about how you have been feeling and any COVID-19 exposures and infections you have had since enrolling in ImmunoCARE. Once you complete this survey you will earn an Amazon gift card to thank you for your time.

Since you enrolled in ImmunoCARE, have you:

	·	
0	Been exposed to a close contact with COVID-19?	[] Yes [] No
0	Contracted COVID-19?	[] Yes [] No
0	Been prescribed medication for COVID-19?	[] Yes [] No
0	Been to Urgent Care due to COVID-19?	[] Yes [] No
0	Been to the Emergency Room due to COVID-19?	[] Yes [] No
0	Been admitted to the hospital for COVID-19?	[] Yes [] No
0	Been in the Intensive Care Unit due to COVID-19?	[] Yes [] No
0	Needed additional health care (e.g. dialysis, CT scar	n, MRI) as a result of
	COVID-19?	

[] Yes [] No

Is there any context you would like to share about your previous responses? (open text box)

Thank you for sharing this information with the study team. Your Amazon gift card is now available.

If No \rightarrow Thank you for confirming you have not had COVID-19 since we last checked in. Your Amazon gift card is now available.

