will be notified by push notification, email and/or SMS (depending on their notification preferences) that their diagnosis has been verified and they are eligible to move forward to participation. Method 3 will be automated back end verification of diagnosis and/or immunosuppressive medication history in MyDataHelps using the participants connected claims data for identification of qualifying ICD-10 diagnosis codes.

[figure not shown]
Study Interventions

All Groups (n=10,000)

Baseline study activities for all groups include: verification of immunocompromised status, downloading MyDataHelps or using the web version, completion of digital informed consent, baseline survey completion, optional connection to claims data source, monthly survey completion and reimbursement for participation.

Control Group (n=5,000)

[figure not shown]
Participants in the control group will complete the baseline study activities, as described above. If symptoms arise or COVID-19 infection occurs, participants will test and seek care as they normally would.

Intervention Arm (n=5,000)

Participants in this group will complete the baseline study activities, as described above. Additionally, participants will be instructed to create a Cue Health account and download the Cue Health App. Using the app and the 10 Cue Health COVID-19 molecular tests that are provided (or Cue Health Flu+COVID molecular tests if available and FDA authorized), the participant will perform tests after exposure or

symptoms arise. Participants can also use the test for close contacts who are exposed to COVID-19 and/or have symptoms. If COVID-19 infection occurs, participants will have access to telemedicine to discuss further with a healthcare professional. When clinically indicated, medication for the treatment of COVID-19 (and/or Influenza in case of Cue Health Flu+COVID test availability) will be prescribed and delivered to the participants' delivery address. Participants can also seek care through other healthcare providers or not seek care, at their discretion.

Device Use and Procedures

CareEvolution MyDataHelps Web or App

MyDataHelps by CareEvolution is the app or website that participants will use for digital consent, surveys, optional connection of claims data and reimbursement. In-app content can be reviewed in the appendices.

The Cue Health Monitoring System

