Participants will be reimbursed for their participation. Total reimbursement will be up to \$2 00 in Amazon gift cards. When the onboarding, informed consent, diagnosis verification, optional claims data sharing process, and baseline survey are complete, participants will be provided with a \$20 Amazon gift card. Participants who do not share claims data will receive \$10 after completing consent and the baseline survey, then \$20 after completing the final survey. Throughout the study, participants will be provided with \$10 Amazon gift cards on a monthly basis for up to 8 months. If the study period runs shorter than 8 months, participants will receive the remaining gift card balance, to total up to \$100, at study closure. Participants who do not share claims data and do not complete all monthly surveys may be offered half of the compensation they missed from monthly surveys upon completion of the final survey. For example, if a participant does not complete three monthly surveys (which would have earned them \$30 of compensation), they may be offered an additional \$15 for completing their final survey. This is to incentivize participants to provide an account of their COVID experiences over the course of the study in the final survey, a crucial data point to achieve study objectives.

Interim analysis for ImmunoCARE has that claims data is more balanced between the two arms than survey data. To collect more claims data , an additional \$100 Amazon gift card will be offered to enrollees for connection of available insurance claims data.

Surveys

Participants will take surveys throughout the course of this study. To determine eligibility, prospective participants will complete the eligibility survey. Once enrolled, participants will complete the baseline survey where we will collect demographic and health information, including comorbidities. Each month, participants will be asked to report on their COVID exposures, diagnoses, and/or hospitalizations. The ability to report the positive diagnosis of a close contact will be available on the participant dashboard at all times. Surveys can be reviewed in the appendices. In an effort toward complete data collection we will collect

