- The number of hospitalizations will be assessed based on survey data. We expect that at least 80% of participants will complete the FINAL SURVEY even if they have been hospitalized.
- The experiment will be run for 4 to 8 months (depending on number of COVID cases), and we expect to have a similar number of COVID-19 cases per month.
- Interim analyses on the number of events and progress towards achieving enough events for a well-powered statistical test significance may be run start at month 1 or later. Determination of ending the study timeline may be based on having sufficient number of COVID cases and/or hospitalization events to achieve statistical power. Importantly, we will utilize data on the total number of events to determine when to

end the experiment; we will not use information on the difference in the number of events between study arms.

Table 2: Sample size (target)

Sample size estimation	Control Arm N=5000	Intervention Arm N=5000
Loss to follow-up / drop-out / failure	5%	5%
Expected total number of COVID-19 positives	540	513
Loss to report: expected ratio of individuals not reporting in survey	20%	20%
Expected total number of COVID-19 positives correctly reported	432	410
Expected total number of reported hospitalizations	102	68
Expected total number reported in ICU	39	26

Given the assumptions of above, we should reach a target of 900 confirmed COVID positive cases reported in the survey or claims (approximately 450 per arm), that we expect to reach in 8 months if the rate of infection remains stable. The statistical power of the test (alpha=0.05) is equal to 0.76, meaning that if all assumptions hold, we have a 76% chance of observing a statistically significant difference in the number of hospitalizations between Control and Intervention arms.

The minimum target is to reach 800 confirmed COVID positive cases (approximately 400 per arm). The corresponding statistical power of the test (alpha=0.05) in this case is less than 0.7, meaning that if all assumptions hold, we have less than a 70% chance of observing a statistically significant difference in the number of hospitalizations between Control and Intervention arms.

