Heading (claims): **Diagnosis Confirmation** Body: The claims data from your health plan indicate a previously diagnosed condition that we need to learn more about for the purposes of this study. Please upload a document confirming your diagnosis on the next screen. This can be a doctor's note, a screenshot of your EHR diagnosis list, lab work, test results or medication list. Accepted file types are [list of file types]. If your document is another type, please email it to the study team at [contact] **Button Text:** Next Heading (no claims): **Diagnosis Confirmation** Body: Thank you for your participation! Please upload a document confirming your diagnosis or age on the next screen. This can be a doctor's note, a screenshot of your EHR diagnosis list, lab work, test results or medication list. Accepted file types are [list of file types]. If your document is another type, please email it to the study team at [contact] **Button Text:** Next

Heading: [None]

Body: [None]

Button Text: Capture or Upload Image
Heading: Thank you
Body: Thank you for confirming your medical information. We will be reviewing the document you uploaded and will notify you when we are ready for you to continue with the study.
Button Text: Done
Heading: Document Review
Body: Our research coordinator is currently reviewing the document you uploaded confirming your diagnosis or age. This process can take a few business days, we appreciate your patience.
No further action is required on your part. We will notify you once we complete our review so you can continue with the study.
Button Text: Done
Heading: Baseline survey
Body: Help us learn about other diagnoses and understand any differences between demographic groups, such as income, race, ethnicity, and age.
Button Text: Next
[Baseline survey questions here; see Appendix 3]

Pre-conditions: Participant randomized into treatment arm
Heading: Thank you
Body: Thank you for sharing this information with the study team.
You have been randomized to the treatment group.
As such, the next step is to register an account with Cue Health and download their app on your smartphone. You will also order your testing kit through the mobile app.
Continue to the next task for additional instructions.
Button Text: Done
Pre-conditions: Participant randomized into control arm
Heading: Thank you
Body: Thank you for completing all of the onboarding activities.
You have been randomized to the control group.

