Appendix 21: ImmunoCARE Animated Explainer Video | Script

INTRO & INCENTIVE

- People who are immunocompromised or over the age of 65 are still at high risk of developing severe disease from COVID-19, but a new study could help reduce that risk.
- The ImmunoCARE study is enrolling 10,000 participants nationwide and is providing some participants with free highly sensitive at-home COVID tests, access to telemedicine and delivery of antiviral medications. All participants will get Amazon gift cards as a thank you for taking part.
- · Interested? Keep watching to learn more, or head to immunocare.scripps.edu to get started.
- Scientists at the Scripps Research Digital Trials Center are investigating if early detection and rapid treatment can reduce COVID-19 hospitalizations among immunocompromised people and those over 65.
- The study is fully remote, meaning you won't need to visit a clinic or have in-person consultations.

ELIGIBILITY & ACCOUNT SET UP

- To find out if you are eligible to participate, you'll need to visit the study website and complete a brief survey.
 - o TEXT ON SCREEN (NOT PART OF SCRIPT):
 - § Live in the United States
 - § 18 years or older

- § Access to smartphone
- § Vaccinated against COVID-19
- § Diagnosed as moderately to severely immunocompromised, or be 65 years or older
- § Willing to participate in all study activities
- If you are eligible to participate, you will be prompted to create an account on the study web app, complete the informed consent process and fill out a short baseline survey.

SYNCING HEALTH PLAN

- Next, you will also be asked to connect to your health plan. This allows scientists to verify your immunocompromised status or age and study any medical care you received through your plan related to COVID-19. We use strict privacy practices.
- If it cannot be verified through your health plan data, you will need to provide proof of your immunocompromised status or age by sharing a document directly with the study team.

INTERVENTION

- Once your status is verified, you will be randomly assigned to either the control arm or the intervention arm. It is important to have participants in both of these groups so scientists can accurately determine whether the intervention is working.
- Those assigned to the control arm will complete a monthly survey about any COVID-19 exposures and diagnosis. If they develop symptoms, they will test and seek care as they normally would.

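### The End of Study Survey looks back to enrolment rather than randomization and asks for no dates, so pre-randomization admissions can enter the arm comparison; the expected effect is modest attenuation

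*Combined protocol and SAP*

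**What the plan says.** - **Look-back of the final survey.** Appendix 3, End of Study Survey: the stem is "Since you enrolled in ImmunoCARE, have you", followed by yes/no items that include infection, emergency room, admission and intensive care. No event date is requested; there is only a free-text box.
- **Enrolment and baseline survey.** Surveys section: "Once enrolled, participants will complete the baseline survey where we will collect demographic and health information, including comorbidities".
- **Randomization.** In the in-app onboarding screens, the message "You have been randomized to the treatment group" follows the baseline survey questions. Appendix 21 says "Once your status is verified, you will be randomly assigned to either the control arm or the intervention arm", and there the baseline survey comes with consent, ahead of health-plan connection and verification.
- **Verification.** The onboarding screens say of document review: "This process can take a few business days, we appreciate your patience". Under Inclusion Criteria, participants whose diagnosis has been confirmed are told that "they are eligible to move forward to participation".
- **Outcome source.** Sample Size and Data Analysis: "The number of hospitalizations will be assessed based on survey data", with the 80% completion assumption tied to the final survey. Study Design names survey and claims data together.
- **Other windows.** Baseline item 11 asks about the last month, including COVID-19 admission. The monthly survey asks about the time since the previous check-in.
- **Status.** Estimated Duration of Study says the study is ending early and that the data will be analysed primarily to describe the pandemic's effect on this population.

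**The concern.** The intervention cannot affect an admission that occurs before assignment. A participant admitted after enrolling but before randomization would truthfully answer yes in the final survey, and that yes cannot be told apart from a later admission. Such events should fall about equally in the two arms. They add the same count to both, pull the event ratio toward 1 and cost power in a design that starts at only 0.76. The same applies to infections, emergency room visits and intensive care stays taken from the final survey.

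The exposure is greatest where other sources are thinnest. Under Reimbursement, participants who share no claims and miss monthly surveys may be paid part of what they missed for completing the final survey. For someone with no claims and no monthly surveys, it is the only self-report after baseline, so no other self-report can date the event.

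**Working it through.** **1. Order of events.** The Surveys section gives enrolment, then baseline survey. The onboarding screens give verification, baseline survey, then arm. Appendix 21 gives baseline survey, verification, then arm. The two disagree on where verification falls, but both put randomization after the baseline survey. Enrolment therefore precedes randomization on either order. The length of the gap is not stated.

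**2. The plan's own power.** Two-proportion z test, two-sided alpha 0.05, pooled variance under the null:

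power = Φ[(p1 − p2 − 1.96·SE0)/SE1]

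- Per case: 450 per arm, p1 = 0.235, p2 = 0.235 × 0.70 = 0.1645. SE0 = 0.02665 and SE1 = 0.02655, so power = Φ[(0.0705 − 0.0522)/0.02655] = 0.754, against the stated 0.76. Reproduced.
- Per participant: 5,000 × 0.95 × 0.80 = 3,800 reporters per arm, with 102 and 68 reported hospitalizations (Table 2). Ratio 68/102 = 0.667, power 0.751.

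**3. Adding pre-randomization events.** Assume admissions before assignment occur at the control rate in both arms, at a constant rate over 8 months (8 × 30.4 = 243.2 days), with a mean gap of g days. Extra events per arm: e = 102·g/243.2. Ratio: (68 + e)/(102 + e). The values of g are assumptions.

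| g (days) | e per arm | Control v intervention | Ratio | Power | Share of intervention events, e/(68 + e) |
|---|---|---|---|---|---|
| 0 | 0 | 102 v 68 | 0.667 | 0.751 | 0% |
| 3 | 1.26 | 103.3 v 69.3 | 0.671 | 0.745 | 1.8% |
| 7 | 2.94 | 104.9 v 70.9 | 0.676 | 0.737 | 4.1% |
| 14 | 5.87 | 107.9 v 73.9 | 0.685 | 0.723 | 7.9% |

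If the gap instead uses up part of a fixed 8-month window, intervention events are 68(1 − g/243.2) + 102·g/243.2, and power is 0.740, 0.724 and 0.696 for the same gaps.

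**4. Shorter follow-up.** With 4 months (121.6 days) and half the events (51 v 34), e is unchanged. The intervention-arm shares e/(34 + e) rise to 3.6%, 7.9% and 14.7%, and the ratios to 0.675, 0.685 and 0.701. Power before any dilution is already only 0.458; it becomes 0.447, 0.434 and 0.413.

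**The case against.** A reader might infer that the protocol places enrolment before verification, so that the whole document-review period lies inside the survey window. No section says so. Enrolment is not defined, and the Inclusion Criteria text treats verification as the gate to taking part. The consent prompts in Appendix 15 and the thanks for joining in Appendix 9 suggest that participants may see consent as the moment they joined, but that is inference. Figure 1, the participant flow, is not shown in the text I worked from and could settle it. If enrolment follows verification, only the time up to the baseline survey remains on the onboarding-screen order.

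A reader might also infer that early admissions are in fact counted and cannot be removed. That goes too far. Claims and monthly surveys also feed the outcome, no rule gives a final-survey yes precedence over them, and baseline item 11 flags many early admissions. What stands is narrower. No rule says how to use these sources, and a yes at both baseline and the end may be one early admission or a second, later one.

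On size, claims verification is automated and prompts begin 5 hours after a step opens, so many gaps may be short. Waiting for the day-7 reminder at both the upload and the baseline survey, plus 3 to 5 business days of review, gives about 17 to 19 days. Reminders are not deadlines, but this is a slow path rather than a likely mean. I accept that the effect is small.

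**Conclusion.** The point holds as a defect in the survey's time origin. The final survey starts its window before randomization, collects no dates, and is not paired with a rule that limits outcome events to those after assignment. The consequence is modest: for assumed mean gaps of 3 to 14 days over 8 months, the ratio moves from 0.667 to between 0.671 and 0.685, and power from 0.75 to between 0.745 and 0.72. These figures rest on the unstated gap, a constant admission rate, and no exclusion of early events by other means, so they are upper values for each gap under the additive model.

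The documents do not support reading this as confounding, since events before assignment are expected to balance between the arms.

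Severity is minor. Early closure raises the affected share of events, but it also makes the remaining analysis primarily descriptive. Any arm comparison still made needs randomization as its time zero.

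**What to change.** - **Final surveys still outstanding:** change the stem to *Since [date you were assigned to your study group]*, with the date pre-filled by the app in both arms.
- **Outcome definition:** add one sentence stating that events in the arm comparison count only from randomization.
- **Returned surveys, claims connected:** use claims dates to exclude admissions before randomization.
- **Returned surveys, no claims:** report a two-way sensitivity analysis. Participants who answered yes to admission at both baseline item 11 and the final survey are counted once as events and once as non-events. Exclusion should not depend on monthly-survey response. The Reimbursement section reports that claims data are better balanced between arms than survey data, so a deletion rule driven by survey response could act differently by arm.

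The cost is one date field, one sentence and one two-way analysis. One limit remains: if the Appendix 21 order was used in practice, item 11 misses admissions between the baseline survey and randomization, so the report should state which order applied.
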